6.3 Instructions for Evaluations

6.3.1 *Medical & Medication History*

At screening, a standard medical history and medication history will be obtained and documented. Specifically, information will be obtained regarding:

- Known allergy/sensitivity or any hypersensitivity to latex or any of the components of the study product or its formulation (see section 5.2 for a list of components).
- Serious illness or injury requiring hospitalization within 21 days prior to study entry.
- A history of a medical condition resulting in impaired immunity (including complement deficiency, antibody deficiency, chronic granulomatous disease, or HIV infection).
- Autoimmune disorders; mild autoimmune disorders such as eczema is not exclusionary after assessment by the investigator.
- Known active infection with HIV, HCV, or HBV.
- History of all cancers including leukemia or lymphoma
- History of excessive alcohol consumption, drug abuse, psychiatric conditions, social conditions, or occupational conditions that in the opinion of the investigator would preclude compliance with the study.
- Hemophilia or other bleeding diatheses.
- Have donated blood or blood products within 30 days before study vaccination, plan to donate blood at any time during the duration of subject study participation, or plan to donate blood within 30 days after the last blood draw.
- Pregnancy in women and nursing mothers or women who are planning to become pregnant within the study duration.
- Prior history of gonorrhea, chlamydia, or syphilis

The medication history will include inquiry and documentation of all medications used within the last 60 days and the participants will be asked specifically about the use of the following agents:

- anticoagulants other than aspirin or nonsteroidal anti-inflammatory drugs (NSAIDS) within 14 days prior to study entry.
- any systemic antineoplastic or immunomodulatory treatment, systemic corticosteroids, (inhaled or topical corticosteroids acceptable), investigational products, interleukins, interferons, growth factors, or intravenous immunoglobulin (IVIG) within 45 days prior to study entry.

The medication history will also include inquiry and documentation of vaccine history and the participants will be asked specifically about the use of the following:

- Previous immunization with a MenB vaccine
- Have received any licensed vaccine within 30 days prior to study vaccination.
- Have planned vaccination with any vaccine within 30 days of the anticipated date of second study immunization (approximately 65 days from study entry).

6.3.2 *Targeted Physical Exam & Vital Signs*

A physical exam performed at each visit will include at a minimum an examination of the skin, head, mouth, and neck; auscultation of the chest; cardiac exam; abdominal exam; and examination of the lower extremities for edema. A targeted physical exam and vital signs (oral temperature, pulse, respiration rate, and blood pressure) including weight will be collected at each visit.

6.3.3 *Laboratory Evaluations*

Pregnancy Test for females of child bearing potential

A point of care pregnancy test is performed and results need to be recorded only in source document at screening visit, at entry, and at week 5 visit prior to vaccine administration.

6.3.4 *Immunologic Studies*

Stored PBMCs

PBMCs for cell-surface marker phenotyping, *N. gonorrhoeae*-antigen stimulated cytokine production, and B-cell receptor cloning will be isolated and stored per the SOE (Schedule of Events). Cryopreserved PBMC will be sent to Duke Immune Profiling Core at Duke University for flow cytometry and cellular immune analysis; the shipped samples will have an identifying sample number (code) derived from the participant's assigned PID and the visit number; no identifying information on the participant's samples will be transmitted to the Duke Immune Profiling Core and leftover samples will be destroyed or returned to UNC for storage if the participant has agreed to storage of their study specimens. The PI at UNC will keep a master log which links the codes on the stored specimens to the participants. Leftover PBMC from consenting participants may be used for future *N. gonorrhoeae* research.

N. gonorrhoeae reactive antibody studies/Stored Serum

Pharyngeal and vaginal swabs, urine, and serum for measures of *N. gonorrhoeae*-directed antibodies will be collected per the SOE. Antibodies eluted from swabs or present in urine and present in serum from samples collected at entry, week 5, week 6, and week 7 will be tested for *N. gonorrhoeae* antigen-specific antibodies using ELISA. Antibody containing samples will be sent to Regional Biocontainment Laboratory (RBL) Immunology Unit at Duke University for ELISA analysis. The shipped samples will have an identifying sample number (code) derived from the participant's assigned PID and the visit number; no identifying information on the participant's samples will be transmitted to the Duke RBL Immunology Unit and leftover samples will be destroyed or returned to UNC for storage if the participant has agreed to storage of their study specimens. The PI at UNC will keep a master log which links the codes on the stored specimens to the participants. Leftover sera from consenting participants may be used for future *N. gonorrhoeae* research.

6.3.5 *Vaccine/ Injection*

Every effort should be made to administer vaccines within the protocol-defined visit window. Participants who do not receive their first vaccine within 30 days of screening or who do not receive the week 5 vaccine will be prematurely discontinued from the study.

The week 5 visit should be conducted 35 days (\pm 7 days) after the first vaccination (enrollment visit). If the week 5 visit is not within the protocol-specified window, then the vaccine can be given as late as 8 weeks post enrollment.

The week 6 visit should occur 5-9 days after the second dose of vaccine; if week 6 visit samples are not collected, the participant may continue in the study and attend the week 7 visit 12-16 days after receiving the second dose of vaccine. If the week 7 visit is not collected between day 12-16 after the second dose of vaccine, participant will be discontinued from the study.

Vaccination should be deferred at the discretion of the site investigator if the participant is febrile with reported or observed temperature greater than or equal to 38 °C or acutely ill with symptoms (ongoing or present within 7 days of planned vaccination) consistent with infection of the respiratory tract, gastrointestinal tract, urinary tract, or skin/soft tissues.

Participants will remain at the clinic for a 15-minute post-injection observation period following each vaccination to observe for syncope or any immediate adverse reactions. Participants will be provided instructions on self-assessment of adverse reactions related to vaccination.

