9.0 STATISTICAL CONSIDERATIONS**9.1 General Design Issues**

This study is a single center, single arm interventional pilot study in which participants will receive two-doses of the US FDA-approved 4CMenB vaccine according to recommended administration schedule. Blood and mucosal surface specimens will be obtained at 4 study visits. The study population will include 15 individuals aged 18-25 years desiring immunization against group B *N. meningitidis* with no contraindication to vaccination and no known immune compromising medical condition or medication. Enrolled individuals who are discontinued will be replaced.

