9.2 Endpoints

9.2.1 Primary Endpoints:

- Geometric mean concentration of IgG binding to *N. gonorrhoeae* strain FA1090 surface antigens (Outer-membrane vesicles) in human serum at entry visit (prior to first vaccination), and week 7 visit (2 weeks after second vaccination) determined by ELISA
- Geometric mean concentration of IgM binding to *N. gonorrhoeae* strain FA1090 surface antigens (Outer-membrane vesicles) in human serum at entry visit (prior to first vaccination), and week 7 visit (2 weeks after second vaccination) determined by ELISA
- Geometric mean concentration of IgA binding to *N. gonorrhoeae* strain FA1090 surface antigens (Outer-membrane vesicles) in human serum at entry visit (prior to first vaccination), and week 7 visit (2 weeks after second vaccination) determined by ELISA
- Frequency of CD4+ T cells expressing at least two different activation markers (IFN-g, TNF-a, IL-2, and CD107a) after in vitro stimulation with *N. gonorrhoeae* strain FA1090 Outer-membrane vesicles in circulating PBMC obtained at entry visit (prior to first vaccination) and week 7 visit (2 weeks after second vaccination) determined by flow cytometry

9.2.2 Exploratory Endpoints:

- Geometric mean concentration of IgM, IgG, and IgA binding to *N. gonorrhoeae* strain FA1090 surface antigens (Outer-membrane vesicles) in human pharyngeal secretions at entry visit (prior to first vaccination), week 5 visit (4-6 weeks after first vaccination), week 6 visit (1 week after second vaccination), and week 7 visit (2 weeks after second vaccination) determined by ELISA
- Geometric mean concentration of IgM, IgG, and IgA binding to *N. gonorrhoeae* strain FA1090 surface antigens (Outer-membrane vesicles) in human vaginal secretions (female participants) at entry visit (prior to first vaccination), week 5 visit (4-6 weeks after first vaccination), week 6 visit (1 week after second vaccination), and week 7 visit (2 weeks after second vaccination) determined by ELISA
- Geometric mean concentration of IgM, IgG, and IgA binding to *N. gonorrhoeae* strain FA1090 surface antigens (Outer-membrane vesicles) in human urine (male participants) at entry visit (prior to first vaccination), week 5 visit (4-6 weeks after first vaccination), week 6 visit (1 week after second vaccination), and week 7 visit (2 weeks after second vaccination) determined by ELISA

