Except for an emergency situation in which proper care for the protection, safety, and well-being of the study participant requires alternative treatment, the study shall be conducted exactly as described in the approved protocol. Any deviation from the protocol must have prior approval by the Principal Investigator and must be recorded and explained.

10.8 **Amendments to the Protocol**

Should amendments to the protocol be required, the amendments will be originated and documented by the Principal Investigator. The written amendment will be approved by the principal investigator and must be submitted to the IRB at the principal investigator's site for approval. It should also be noted that when an amendment to the protocol substantially alters the study design or the potential risk to the participant, a revised consent form might be required.

10.9 **Data Management**

Data to be obtained during the study includes directed medical history provided by participant self-report, personally identifying information (including name, contact information, results of directed physical examination, and point of care pregnancy tests administered to female participants, as well as results of research tests to monitor immunologic response to immunization. Medical history and personal identification information will be recorded with identifiers and kept in participants' research charts. After written informed consent is provided, consecutive study code numbers will

be assigned to the participants to ensure confidentiality. This study code number will be used to identify research specimens and the results of research tests. At the end of each individual's participation in the trial, research charts will be reviewed by the study coordinator and stored in locked cabinets in the PI's office. At the completion of the study, the research charts and all identifying information related to participants will be archived in an off-site storage facility.

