The site principal investigator will make study documents (e.g., consent forms, drug distribution forms, CRFs) and pertinent hospital or clinic records readily available for inspection by the local IRB, the site monitors, the FDA, the NCATS, the OHRP, or NC TraCS for confirmation of the study data.

10.12 **Participant Confidentiality**

All laboratory specimens and accompanying evaluation forms, reports, and other records that are sent to Duke University for immunologic analysis will be de-identified to maintain participant confidentiality. All records will be kept locked in secure areas/secure offices at UNC. All

computer entry and networking programs at UNC will be done with coded numbers only. Clinical information will not be released without written permission of the participant, except as necessary for monitoring by the IRB, the NCATS, the OHRP, or NC TraCS.

10.13 **Study Discontinuation**

The study may be discontinued at any time by the IRB, NCATS, the OHRP, NC TraCS or other government agencies as part of their duties to ensure that research participants are protected.

11.0 **BIOHAZARD CONTAINMENT**

As the transmission of HIV and other blood-borne pathogens can occur through contact with contaminated needles, blood, and blood products, appropriate blood and secretion precautions will be employed by all personnel in the drawing of blood and shipping and handling of all specimens for this study, as currently recommended by the Centers for Disease Control and Prevention and the NIH.

All dangerous goods materials, including diagnostic specimens and infectious substances, must be transported using packaging mandated by CFR 42 Part 72. Please refer to instructions detailed in the International Air Transport Association (IATA) Dangerous Goods Regulations.

12.0 **REFERENCES**

- 1 Tapsall, J. W. Antibiotic resistance in *Neisseria gonorrhoeae*. *Clin Infect Dis* **41 Suppl 4**, S263-268, doi:10.1086/430787 (2005).
- 2 Unemo, M. *et al.* High-level cefixime- and ceftriaxone-resistant *Neisseria gonorrhoeae* in France: novel penA mosaic allele in a successful international clone causes treatment failure. *Antimicrob Agents Chemother* **56**, 1273-1280, doi:10.1128/AAC.05760-11 (2012).
- 3 European Centre for Disease Prevention and Control. Extensively drug-resistant (XDR) *Neisseria gonorrhoeae* in the United Kingdom and Australia. (2018).

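### Samples are coded from PID and visit number and nothing masks the laboratories to visit: an avoidable bias risk of unknown size, mainly for the CD4+ flow endpoint

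*Combined protocol and SAP*

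**What the plan says.** Section 6.3.4 applies the same code rule twice. PBMC for flow cytometry and cellular analysis leave UNC under a code formed from the participant's "assigned PID and the visit number; no identifying information on the" participant's samples reaching the core laboratory. The antibody samples, sent to the "Immunology Unit at Duke University for ELISA analysis", carry a code formed in the same way. The format of the code is not given.

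The rest of the coding text concerns identity. Section 6.3.4 adds: "The PI at UNC will keep a master log which links the codes on the stored specimens to the participants". Section 10.9 says that consecutive code numbers will "be assigned to the participants to ensure confidentiality", and then: "This study code number will be used to identify research specimens and the results of research tests". Section 10.12 says that specimens and the "accompanying evaluation forms, reports, and other records that are sent to Duke University for immunologic analysis will be de-identified to maintain participant confidentiality".

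Sections 9.2.1 and 9.5.1 define the primary analysis as a within-person comparison of entry with week 7, by paired t-test or Wilcoxon test, with emphasis on point estimates and 80% confidence intervals. Three primary endpoints are serum ELISA concentrations (IgG, IgM, IgA). The fourth is the "Frequency of CD4+ T cells expressing at least two different activation markers", measured by flow cytometry.

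**The concern.** Coding for confidentiality hides who the participant is. Masking for measurement hides when the sample was taken. The plan provides the first and is silent on the second, while building the code partly from the visit number.

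This matters more here than in a controlled trial. If readers favoured later samples, even without meaning to, a control arm would show the same drift and reveal it. With one arm, a systematic difference in how entry and week 7 samples are read cannot be separated from a vaccine response. Section 9.5.2 intends the results to guide how these assays are used in later efficacy work, so a reading artefact could carry forward.

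**Working it through.** **1. Is there masking anywhere?** Sections 6.2, 6.3.4, 9.1 to 9.5, 10.9 and 10.12 were read together. What is withheld from the laboratories is participant identity (6.3.4, 10.12). The log ties codes to participants (6.3.4) and is not described as concealing visit. No section masks a reader to time point, randomises run or read order, or fixes flow gates before visit is known. Batch running (6.2.2, 6.2.3, 9.3) limits drift between runs, but does not hide visit from whoever reads the batch.

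**2. Which endpoints depend on a reader?**
- Primary: 1 of 4, the CD4+ flow endpoint. No gating rule is given. The comparison uses 8 × 2 = 16 to 15 × 2 = 30 PBMC samples (at least 8 complete sets, up to 15 enrolled; section 9.3).
- Exploratory: the CD8+ and Tfh flow frequencies, and the immunoblot, which section 9.2.2 calls qualitative. The place where blots are read is not stated.
- Less exposed: the three ELISA primary endpoints, reported as concentrations.

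**3. Scale, as a hypothetical only.** There is no plan figure to reproduce: section 9.5.2 says power is unknown, and no SD is given. Assume zero true change, roughly normal paired differences, a t-based 80% interval, and a reading shift of *d* SD of the paired differences. The values of *d* are assumptions.

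Half-width in SD = t(0.90, n−1)/√n:
- n = 8: 1.415/2.828 = 0.50
- n = 15: 1.345/3.873 = 0.35

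The chance that the interval misses zero follows from the noncentral t distribution with n−1 degrees of freedom and noncentrality d√n:

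| n | d | d√n | wholly above 0 | wholly below 0 | either |
|---|---|---|---|---|---|
| 8 | 0 | 0 | 10.0% | 10.0% | 20.0% |
| 8 | 0.1 | 0.283 | 15.5% | 6.1% | 21.6% |
| 8 | 0.2 | 0.566 | 22.7% | 3.5% | 26.2% |
| 15 | 0 | 0 | 10.0% | 10.0% | 20.0% |
| 15 | 0.1 | 0.387 | 18.3% | 4.9% | 23.1% |
| 15 | 0.2 | 0.775 | 29.8% | 2.1% | 31.9% |

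(Sums may differ by 0.1 through rounding.)

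Simulation (400,000 runs) with heavier-tailed differences (t, 5 df) gives similar either-direction figures: 22.0% and 27.6% at n = 8, 23.9% and 33.9% at n = 15, for d = 0.1 and 0.2. With strongly right-skewed differences (standardised lognormal, sigma 0.8) the interval already misses zero in 26.6% (n = 8) and 24.8% (n = 15) of runs with no shift at all. The table therefore applies only to near-symmetric differences. The documents do not say what shape the CD4+ differences have.

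**The case against.** The strongest reply is that the point rests on silence. Harm needs a chain: visit can be read from the code, the reader notices it, gating leaves room for choice, and the resulting shift is systematic. None of these links is shown. A laboratory manual may already mask visit, PBMC go to a core at another institution, and the study is a pilot with no success rule that turns on an interval excluding zero.

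Much of this stands. It limits the point to a risk of unknown size and rules out using the table as an estimate. It does not remove the point. The protocol neither states masking nor refers to a manual that does. An outside laboratory can read a visit number as easily as a local one. Pilot status and wide intervals do not protect a point estimate from systematic error.

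A second reply is that recoding should be confined to PBMC, since ELISA is less exposed. But the immunoblot uses serum, so serum needs recoding too; swabs and urine are included only for uniformity.

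A third reply is that relabelling has its own hazard, and this is right. Swapping one participant's entry and week 7 samples turns a difference D into −D and moves the mean by 2D/n: 2/8 = 0.25 D at n = 8, or 2/15 = 0.13 D at n = 15. That calls for a check before shipment.

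**Conclusion.** The point holds as a cheap improvement in design. Nothing in the protocol masks the laboratories to visit, visit is the only contrast, and the code is built partly from the visit number. The exposure is mainly the CD4+ flow primary endpoint, with the exploratory flow and immunoblot endpoints.

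Two stronger readings should be avoided. A reader might infer that the laboratories will know the visit; the text says only that the code is derived from PID and visit number, and leaves open whether visit can be read back. A reader might also take the percentages above as the expected false-positive rate for the CD4+ endpoint. They are not: the shifts are assumed, the plan has no decision rule tied to the interval, and the figures fail for skewed differences. The size of any bias cannot be derived from these documents. If masking is already in place elsewhere, a sentence in section 6.3.4 saying so settles the matter.

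**What to change.** Replace the code rule in both paragraphs of section 6.3.4, for example:

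*PBMC, serum, swabs and urine are shipped under random codes that reveal neither visit nor collection date; accompanying forms show neither. A participant grouping label allows one participant's samples to be run together in random order. The code-to-visit key is kept in the UNC log by a person who reads none of the assays. Flow gates, immunoblot calls and repeat-run decisions are locked before visit is released. Codes are checked against the log before shipment.*

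B-cell receptor sorting and cloning is not a pre/post comparison. It may be exempt, provided visit is not disclosed to those reading the other flow endpoints before their gates are locked.

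Cost: 15 participants × 4 visits × 4 specimen types = 240 specimens to relabel at full enrolment, before aliquots. Section 9.1 states: "Enrolled individuals who are discontinued will be replaced". Each replaced participant sampled at 1 to 3 visits therefore adds 4 × 1 = 4 to 4 × 3 = 12 specimens. The log gains a code-to-visit column, and the data flow gains a lock step and the pre-shipment check. The principal investigator, who keeps the log, can hold the key only if that person reads no assay; otherwise a separate key holder is needed. No visit, participant or assay is added.

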6.3.6 Telephone Contact

The study staff will contact each participant by telephone 48 to 72 hours after each vaccination at the entry visit and at the week 5 visit to determine whether any side effects have occurred. Information from the telephone contact will be recorded on the electronic case report form (eCRF). If a participant experiences any side effects that are Grade 3 or 4, including edema (swelling), erythema (redness), or induration of the injection site, the participant should be scheduled to come into the research clinic for evaluation, including a targeted physical exam focused on the area involved, as soon as possible.

NOTE: If telephone contact is not possible, then in person is permissible.

7.0 CLINICAL MANAGEMENT ISSUES

7.1 Dose Modification

No modification of the study vaccine dose is allowed.

7.2 Toxicity Management

7.2.1 *Management of Injection Site and Allergic Reactions*

Local and systemic reactions will be graded according to the DAIDS Adverse Event (AE) Grading Table, Corrected Version 2.1, July 2017, found on the DAIDS RSC Web site: <http://rsc.tech-res.com/safetyandpharmacovigilance/>.

Injection Site Reactions

- Swelling, induration, or redness at the injection site
- Pain or tenderness, or other reactions at the injection site

Systemic reactions occurring within 48 hours after vaccination

- Fever or chills
- Malaise or fatigue
- Headache or pain, e.g., myalgia or arthralgia
- Nausea or vomiting
- Allergic reactions, e.g., rash, hives, dyspnea, pruritis

For any Grade 3 or 4 reactions thought definitely, possibly, or probably related to vaccination, further vaccines should not be given to that participant. The participant will be asked to return to the site for an evaluation and followed until AE has been resolved.

7.2.2 *Other Adverse Events*

For toxicities not specifically addressed above, the following guidelines should be used for the management of AEs that are felt to be at least possibly related to vaccines:

Grade 1 or 2 Toxicity/AE:

Participants who develop a Grade 1 or 2 AE may continue in the study and receive the second dose of vaccine (which may be postponed as directed in section 6.3.5) and return for evaluation study visits as noted in section 6.2.3. For participants experiencing Grade 1 or 2 AEs who choose to discontinue study treatment or study participation prior to receiving the second vaccine dose, see section 6.2.4.

Grade 3 or 4 Toxicity/AE:

Participants who develop a Grade 3 or 4 AE that is at least possibly related to vaccine should be re-evaluated for that toxicity until the AE returns to Grade ≤ 2 . Participants who experience Grade 3 or 4 AE that is at least possibly related to vaccine should not receive the second immunization if the AE occurs prior to the week 5 study visit and their participation in the study should be discontinued. Participants who experience a grade 3 or 4 AE that is considered by the investigator to be unrelated to vaccine or that occurs after the second immunization may continue in the study and study specimens may be obtained for week 6 and 7 visits if the AE has returned to Grade ≤ 2 . For instructions regarding participants experiencing Grade 3 or 4 AEs that are at least possibly related to vaccine that result in premature discontinuation of study vaccine and/or study participation, see section 6.2.4. These participants should be followed until resolution of the AE Toxicity.

